#### 8. Statistical analyses

#### 8.1 Plan of analysis

The data will be analysed according to the intention to implement a surgical step and will be reported in accordance with the principles of the CONSORT guidelines (but not items relating to randomization). A detailed statistical analysis plan will be prepared prior to locking the database. The primary outcome, time to PSH (defined as the time when PSH confirmed by imaging) and secondary time-to-event outcomes, will be analysed using survival methods. The models will take account of the hierarchical structure of the data; i.e. participants, nested within surgeons nested within centres. The hazards of key predictors will be estimated, with 95% confidence intervals, after adjusting for important procedure, patient and surgeon confounding factors.

Exploratory analyses will be used to inform the choice of survival distribution (e.g. Weibull). The factors included in the model, the modelling strategy and the approach to handling correlated covariates will be documented in the statistical analysis plan. Participants free from a PSH at final follow-up will be censored. Follow-up will also be censored if bowel continuity is restored, if participants have a redo stoma or die. These circumstances leading to censoring may be informative and sensitivity analyses (setting survival times to the longest observed times) will be undertaken to assess the potential impact of informative censoring. Secondary continuous outcomes will be analysed using a mixed regression models, again taking account of the hierarchical structure of the data and the repeated measurements over time. Binary outcomes (e.g. complications) will be analysed using

logistic regression. If the frequency of the outcomes allows, these models will also take account of the hierarchical structure of the data.

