#### 2. Background

In the UK approximately 20,000 new stomas are created annually [1]. Within two years of the initial stoma formation, up to 40% of patients may have developed a PSH. This means that there is a swelling next to the stoma whereby abdominal contents protrude underneath the skin. While some PSHs are asymptomatic, it is thought that at least 50% are associated with problems. The most common symptoms are pain (35%) and difficulty attaching the stoma appliance (28%) [3]. This may result in the leakage of bowel contents (28%), which can cause skin irritation, anxiety and embarrassment [3]. Some patients require emergency

admission to hospital due to bowel obstruction, strangulation or perforation. This may necessitate surgery, potentially including revision of the stoma, which can be associated with the development of further PSH. Prevention of PSH is therefore a priority. Indeed this was recently supported by a Delphi survey of the Association of Coloproctology of Great Britain and Ireland (ACPGBI), who ranked optimisation of methods to prevent and repair PSH as a key research question [4].

The NIHR has funded the UK Cohort study to Investigate the prevention of Parastomal Hernia (CIPHER). CIPHER is designed with two parts (Phase A and B). Phase A involves essential preliminary work before the cohort study can take place (Phase B). Phase A will identify the data that should be collected in order to investigate the prevention of PSH. This includes information about surgical technique (Part 1) and development of a patient-reported outcome measure (Part 2).

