#### 4.6 Primary and secondary outcomes

#### 4.6.1 Primary outcome

The primary outcome will be PSH incidence during follow-up after index surgery to form a stoma. An incident PSH is defined as:

- Symptoms of PSH (see 5.4), and
- Anatomical PSH, ascertained by independent reading of a CT scan (6)

Participants will describe their PSH symptoms using a custom-designed questionnaire, the "stoma questionnaire" [34]. Symptoms will be classified as green (asymptomatic), amber (mild/moderate symptoms) or red (severe symptoms). Cut-off points for these classifications will be defined on the basis of on-going data collection. We anticipate that severe symptoms may include recurrent problems with the stoma appliance, pain, or admission to hospital with obstruction. Mild/moderate symptoms are likely to be associated with discomfort and ill-fitting appliance issues managed by the patients themselves.

CT scans carried out in the course of a patient's usual NHS care will be assessed for all participants, with anatomical PSH being graded using the EHS classification (EHS class I, II, III or IV [24]). CT scans taken up to 6 months before or 3 months after the stoma questionnaire is completed will be valid for assessing anatomical PSH. The combination of symptomatic PSH and anatomical PSH confirmed by CT imaging will be our primary outcome. CT assessors will collect additional details from CTs (e.g. linear measurement of the PSH defect rather than just defect size >5cm vs ≤5cm), including a measure of the size of the PSH. The ESH criteria for classifying PSH as small or large will be reviewed on the basis of these additional data as the study progresses.

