#### 4.6.2 Secondary outcome measures

Secondary outcomes include:

- 1. Intensive care unit (ICU) stay (days) during admission for index surgery
- 2. Hospital stay (days) during admission for index surgery and associated costs
- 3. Surgical site infection during admission for index surgery and 30 days afterwards
- 4. Other complications, documented using the Clavien Dindo classification [35] and the Comprehensive Complication Index [36, 37]
- 5. Questionnaire to assess symptoms of PSH (developed in Phase A; REC 16/EM/0155)
- 6. Generic health status (EQ-5D-5L, SF12 [38, 39]), which will be combined with survival to estimate QALYs
- 7. Appointments with SCNs, stoma care products used and associated costs
- 8. PSH repair (procedure codes for stoma formation in HES, information from SCNs) and associated hospital costs
- 9. Estimated cost of hospital care during follow up and primary care, social care and societal costs associated with stoma.

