#### 5.10 Likely rate of loss to follow-up

In accordance with **Figure 1**, we expect that ≥90% of patients will complete follow-up or die within the minimum 2 year follow-up period, i.e. loss to follow-up of <10% for the primary outcome for reasons other than death. We will make all reasonable efforts to stay in contact with patients through the use of postal communication, email, text message and telephone. We will also use multiple sources to track participants during follow-up (see 5.4). About a further 15% are expected to die within two years; the reduced follow-up for these participants may impact on the power of the study to detect associations between PSH and surgical variants, depending on whether death occurs before or after ascertainment of a PSH. The impact of attrition due to death on the power of the study will be reviewed as data accrue to ensure that the study can address the objectives satisfactorily.

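### For a redo stoma done because of an unconfirmed hernia, the censoring rule and its only named sensitivity analysis err in the same direction; two-year incidence also needs a competing-risk estimate

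*Protocol*

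**What the plan says.** Protocol (Phase B) section 8.1 fixes both the censoring rule and the check on it. The rule is: "Follow-up will also be censored if bowel continuity is restored, if participants have a redo stoma or die". The check is: "These circumstances leading to censoring may be informative and sensitivity analyses (setting survival times to the longest observed times) will be undertaken". Section 8.1 leaves model factors, modelling strategy and correlated covariates to the statistical analysis plan, but it states these two items itself.

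The event is "time to PSH (defined as the time when PSH confirmed by imaging", and section 4.6.1 requires both symptoms on the stoma questionnaire and an anatomical PSH on CT. On timing, "CT scans taken up to 6 months before or 3 months after the stoma questionnaire is completed will be valid". Table 4 schedules the stoma questionnaire at 6 months, 12 months and 6-monthly after that. CT scans are those taken in usual care.

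Surgery for PSH is collected separately as a secondary outcome: "PSH repair (procedure codes for stoma formation in HES, information from SCNs" (section 4.6.2). It is neither a primary event nor a reason for censoring. The Phase A background (section 2) links emergency admission with complications to re-operation: "This may necessitate surgery, potentially including revision of the stoma". On mortality, section 5.10 says: "About a further 15% are expected to die within two years", and discusses the effect on power only. Objective 1 (section 3) is the incidence of PSH within 2 years.

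**The concern.** Censoring treats a participant who leaves the risk set as having the same later hazard as those who stay. A stoma redone because of a hernia breaks that assumption, since the reason for leaving is the outcome itself. If the hernia had not yet met the symptoms-plus-CT definition, the participant enters the analysis as PSH-free up to the redo. The one named check then makes the participant PSH-free up to the longest time in the study. A check that pushes the estimate further the same way cannot show how large the problem is.

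Death and restored continuity raise a different issue. They end the possibility of a PSH, so an incidence obtained by censoring them is the risk in a population where nobody dies or is reversed. Objective 1 reads as a description of what happens to patients, which is the cumulative incidence with those events competing.

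At stake are the two-year incidence and, if such redos are commoner with one technique than another, the hazard ratios between techniques.

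**Working it through.** **1. The plan's own figure.** Table 3, exposure 1:1, squared correlation 0, incidence 40%, 4,000 participants, 5% two-sided: HR = exp[(z₀.₉₇₅ + z_power) / √(N × incidence × p(1−p))].
- 90% power: exp[(1.960 + 1.282) / √(4000 × 0.40 × 0.25)] = exp(3.242/20) = 1.18.
- 80% power: exp[(1.960 + 0.842)/20] = 1.15.

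Both match Table 3. The protocol gives no figure for the effect of censoring.

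**2. Where an event can be missed.** A PSH confirmed before the redo is an event. One can be missed in these situations:
- The redo takes place before month 6, so no stoma questionnaire exists before censoring.
- The CT is taken more than 3 months after the last questionnaire. Only the next questionnaire could validate it, and that falls after the redo.
- The last questionnaire was free of symptoms and the hernia became symptomatic afterwards.

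A PSH repair without a qualifying pair does not censor the participant, who stays at risk as PSH-free.

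**3. Death.** Inputs: two-year PSH risk F = 30% or 40% (section 4.7) and 15% deaths (section 5.10). Assumptions: constant, independent hazards. h = −ln(1−F)/2, d = −ln(0.85)/2, cumulative incidence = h/(h+d) × [1 − (1−F) × 0.85].
- F = 30%: h = 0.1783, d = 0.0813. 0.1783/0.2596 × (1 − 0.595) = 27.8%. Censoring deaths gives 30%, which is 2.2 points higher.
- F = 40%: h = 0.2554. 0.2554/0.3367 × (1 − 0.51) = 37.2%. Censoring gives 40%, which is 2.8 points higher.

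Moving deaths to the longest time keeps them in the denominator without an event, which gives the same 27.8% and 37.2%. The same algebra holds for restored continuity, for which no rate is given.

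**4. Redo for an unconfirmed PSH.** Let q be the share of PSH cases redone before confirmation. The documents give no value, so 5%, 10% and 20% are assumptions. With no deaths and the redo at PSH onset:
- Censoring: the observed event hazard is (1−q)h, so the estimate is 1 − (1−F)^(1−q).
- Longest-time check: missed cases stay as non-events, so the estimate is F(1−q).
- Redo counted as an event: the estimate is F.

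| True | q | Censoring | Longest-time check |
|---|---|---|---|
| 30% | 5% | 1 − 0.70^0.95 = 28.7% | 28.5% |
| 30% | 10% | 1 − 0.70^0.90 = 27.5% | 27.0% |
| 30% | 20% | 1 − 0.70^0.80 = 24.8% | 24.0% |
| 40% | 5% | 1 − 0.60^0.95 = 38.4% | 38.0% |
| 40% | 10% | 1 − 0.60^0.90 = 36.9% | 36.0% |
| 40% | 20% | 1 − 0.60^0.80 = 33.5% | 32.0% |

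A simulation of 400,000 participants per scenario agrees to within 0.1 point (for example 28.8% in the first row). In every row both estimates lie below the truth.

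**5. Both together** (F = 40%, 15% deaths, q = 10%, simulated): true cumulative incidence 37.3%, censoring 37.0%, longest-time check 33.6%.

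**6. Technique comparisons.** If 10% of events are lost equally in both groups, the detectable HR at 90% power moves from 1.18 to exp[3.242/√(1440 × 0.25)] = 1.19. If 20% are lost in one group and 5% in the other (assumed), the HR is multiplied by 0.80/0.95 = 0.84.

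**The case against.** Several points on the other side are sound.

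- **Confirmed hernias count.** A reader might infer that the worst hernias are lost, or that every repair or redo is scored as a non-event. The documents do not support that. Only hernias operated on before a qualifying questionnaire and CT pair are missed.
- **The named check is right for death and reversal.** A reader might infer that it makes matters worse in general. For these two reasons it gives the competing-risk figure, so it should stay. The criticism applies to PSH-related redo only.
- **No rate is given.** The link from PSH to redo rests on hedged Phase A background. Phase B section 2.2.1 calls strangulation, obstruction and perforation rare. The 5% to 20% is illustrative.
- **No estimator is named for objective 1.** Section 8.1 speaks of survival methods and hazards, and censoring competing events is standard for cause-specific hazards. The analysis plan may name a cumulative incidence.
- **Repairs are weak as primary events.** Section 2.2.2 says the number of repairs is unknown because coding varies. Such events would have no independent CT grade. Section 4.8 says the CT assessors do not know the technique but gives no such assurance for those deciding on surgery.

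These points narrow the concern. They do not answer the specific gap: section 8.1 itself concedes informative censoring and then names a check that cannot detect this form of it.

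**Conclusion.** The point holds in a limited form. For a redo stoma done because of a PSH not yet confirmed, the main analysis and the only named sensitivity analysis err in the same direction. If 5% to 20% of PSH cases were affected, the main estimate would be low by about 1 to 6 points and the check by about 1.5 to 8 points. These sizes rest on an assumed share, constant hazards and a redo at the time of PSH onset.

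Separately, if objective 1 were estimated by censoring deaths, the two-year incidence would be overstated by 2.2 to 2.8 points at the protocol's own 15% mortality. The existing check already shows that gap.

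A reader might infer that the reported incidence is biased in a known direction. It is not: deaths push it up, missed redos push it down, and in the combined scenario they nearly cancel (37.0% against 37.3%). With neither the redo nor the reversal rate known, cancellation cannot be relied on. Equal loss across techniques hardly affects power; unequal loss could matter, but nothing in the documents shows that it will occur.

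**What to change.** 1. In section 8.1, keep the symptoms-plus-CT primary definition and the longest-time analysis. Add a named sensitivity analysis in the opposite direction, in which PSH repair, or redo stoma with PSH as an indication, counts as an event at the procedure date. Use the HES and stoma care nurse data already collected, and fix the code list and the rule for assigning the indication before database lock.
2. State that the two-year incidence in objective 1 is reported as an Aalen-Johansen cumulative incidence with death and restored continuity as competing events. Keep cause-specific hazards for the technique comparisons.

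The cost is some wording and standard software, with no new data collection. The downside is that repairs and redo indications are unevenly coded and these events lack an independent CT grade. That is why they belong in a sensitivity analysis and not in the primary outcome.

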#### 3. Aims and objectives

The CIPHER study (Phase B; CIPHER-B) aims to establish the incidence of symptomatic and radiologically confirmed PSH during a minimum of 2 years follow up. Additionally, CIPHER aims to evaluate the effects of key technical surgical steps during index stoma formation on the risk of subsequent PSH formation.

Specific objectives of CIPHER-B are:

- 1. To describe the incidence of PSH formation within 2 years of formation of all types of stomata other than loop ileostomies;
- 2. To describe the risk of PSH for different types of stoma (end colostomy versus loop colostomy versus end ileostomy)
- 3. To describe the risk of PSH according to how the stoma trephine is created in the anterior fascia of the abdominal wall with respect to location (within or without the rectus sheath) and shape (cross versus circle versus slit);
- 4. To describe the relative risk of PSH following index stoma creation with or without mesh (no prophylactic mesh versus biologic mesh versus synthetic mesh);
- To describe the relative risk of PSH following index stoma creation with prophylactic mesh according to mesh position (intra-abdominal versus sublay/retrorectus versus. onlay);
- 6. To describe the relative risk of PSH with different trephine shapes in the mesh (circle versus cross versus slit versus none (Sugarbaker)).
- 7. To estimate the cost effectiveness of commonly used types of mesh (e.g. biologic, synthetic) versus no prophylactic mesh in prevention PSH and improving health related quality of life.

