#### 4.7 Justification of target sample size

The target sample size currently assumes an attrition rate of 10% at two years after index surgery. In practice, the power of the study will be increased by follow-up longer than two years for a proportion of participants and decreased by follow-up shorter than two years for a proportion (e.g. due to mortality, participants requesting to withdraw, or planned closures of loop ileostomies). These factors will be monitored as data accrues for the study, their consequences for the target sample size will be modelled and the target sample size revised if appropriate.

We have estimated the hazard ratio that the study will be able to detect for a range of scenarios. The incidence of PSH is unknown; we have considered incidences of 30% and 40% as plausible. Surgical methods of interest are used with varying frequencies and so we have considered the impact of a range of ratios for the use of technical variation when comparing one variation with another, i.e. ratios of 1:1, 1:2, 1:5, 1:10 and 1:20. The correlation of the exposure of interest with other covariates is also unknown and we considered the impact of a range of correlations (0, 0.3 and 0.5). The hazard ratios that can be detected from a study of 4000 participants at the 5% level (2-sided) are shown in **Table 3**. For simplicity, we have assumed a binary exposure variable. For multi-category exposures, we will assess the overall effect of the exposure; if we were to adjust the significance level from 5% to 2% to allow for comparisons between subcategories, the power reduces from 90% (80%) to 82% (68%).

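### If the 2-year incidence and the risk by stoma type are read from the analysis that censors death, restored continuity and redo stoma, they will overstate how many patients develop a parastomal hernia, by about 2 to 3 points on the protocol's own figures

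*Protocol*

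**What the plan says.** Section 4.6.1 defines the main endpoint as an incidence: "The primary outcome will be PSH incidence during follow-up after index surgery to form a stoma". In section 3, objective 1 is "To describe the incidence of PSH formation within 2 years of formation of all types of stomata other than loop ileostomies", and objective 2 asks for the risk in end colostomy, loop colostomy and end ileostomy. Both are absolute quantities.

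Section 8.1 says the primary outcome is analysed as time to PSH by survival methods. Participants free of PSH at their last follow-up are censored, and then: "Follow-up will also be censored if bowel continuity is restored, if participants have a redo stoma or die". The same section accepts that this censoring may be informative and adds that "sensitivity analyses (setting survival times to the longest observed times) will be undertaken to assess the potential impact of informative censoring". The only estimates it names are relative: "The hazards of key predictors will be estimated, with 95% confidence intervals, after adjusting for important procedure, patient and surgeon confounding factors". It names no estimator for the absolute 2-year incidence, and no cumulative incidence function or competing-risk method appears anywhere in the protocol.

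For size, section 5.10 expects that "About a further 15% are expected to die within two years", and section 4.7 says: "The incidence of PSH is unknown; we have considered incidences of 30% and 40% as plausible".

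**The concern.** A participant who has died, has had continuity restored or has had the stoma re-made can no longer develop a PSH at the index stoma. These are competing events, not ordinary losses to follow-up. Censoring them assumes that these participants would have gone on to PSH at the same rate as those still at risk. The complement of the Kaplan-Meier curve, or the risk from a fitted Weibull model, then describes a population in which nobody dies or is reversed.

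That is a legitimate basis for a cause-specific hazard ratio. It does not answer how many patients will have had a PSH by 2 years, which is what objective 1 asks and what patients and commissioners would take the figure to mean. Section 8.4 itself speaks of the 30% to 40% as a share of participants who will have developed a PSH.

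For objective 2, the overstatement depends on how often each stoma type is closed and how often its patients die. Two types could show the same censored risk while clearly different proportions of their patients develop a PSH.

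**Working it through.** **1. The protocol's own figures.** Section 4.7 gives no absolute-risk calculation to reproduce, but Table 3 shows how the 30% and 40% are used. With events = N × incidence, detectable HR = exp[(z₀.₉₇₅ + z_power) / √(N × incidence × p(1−p)(1−R²))]. For N = 4,000, 40%, 1:1 and R² = 0, the square root is √(4000 × 0.40 × 0.25) = 20:
- 90% power: z-values 1.960 and 1.282 sum to 3.242, and exp(3.242 ÷ 20) = 1.18
- 80% power: z-values 1.960 and 0.842 sum to 2.802, and exp(2.802 ÷ 20) = 1.15

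Both match, and all 60 cells agree to within about 0.005. Table 3 thus treats 40% as 1,600 PSH events among 4,000 people, that is, as an observed proportion.

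**2. Formula.** Assume constant, independent cause-specific hazards over 24 months. Let F be the censored estimate, d the 2-year death proportion and q the net 2-year closure proportion. With H = −ln(1−F), D = −ln(1−d) and C = −ln(1−q):

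Actual cumulative incidence = H/(H+D+C) × [1 − (1−F)(1−d)(1−q)]

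F = 0.30 or 0.40 is from section 4.7 and d = 0.15 from section 5.10. The protocol gives no q, so 0 to 0.50 is an assumed range.

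**3. Deaths only (q = 0, D = 0.1625).**
- F = 0.30: H = 0.3567 and H+D = 0.5192, ratio 0.687; times (1 − 0.70 × 0.85) = 0.405 gives 0.278, a gap of 2.2 points
- F = 0.40: H = 0.5108 and H+D = 0.6733, ratio 0.759; times (1 − 0.60 × 0.85) = 0.490 gives 0.372, a gap of 2.8 points

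Read the other way, an actual 30% would be reported as 32.3% and an actual 40% as 43.0%.

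Timing matters. For F = 0.40, the gap would tend to zero if all deaths came at the end of the 2 years. It would reach 0.15 × 40 = 6 points if they all came at the start.

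**4. Adding closure (assumed net share by 2 years, 15% deaths).**

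| Closed by 2 years | Censored 30% corresponds to | Censored 40% corresponds to |
|---|---|---|
| 0% | 27.8% | 37.2% |
| 10% | 26.5% | 35.5% |
| 30% | 23.8% | 31.9% |
| 50% | 20.7% | 27.85% |

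Example, last cell: H = 0.5108, D = 0.1625 and C = 0.6931, so H/(H+D+C) = 0.3738; times (1 − 0.60 × 0.85 × 0.50) = 0.745 gives 0.2785.

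**5. Two stoma types with the same PSH hazard.** Both show a censored 40%. With 15% deaths, a type with 2% closure has an actual risk of 36.8% and a type with 50% closure 27.85%. That difference of about 9 points is invisible in the censored figures.

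**6. The planned sensitivity rule.** A simulation of 400,000 participants per scenario, with follow-up ending at 2 to 4 years, moved everyone with a competing event to the longest observed time:

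| Scenario | Sensitivity rule | Cumulative incidence |
|---|---|---|
| F = 30%, deaths only | 27.9% | 27.8% |
| F = 40%, deaths only | 37.1% | 37.2% |
| F = 30%, 30% closure | 23.7% | 23.8% |
| F = 40%, 30% closure | 31.8% | 31.9% |

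With 10% loss to follow-up added, the rule stayed within about 0.3 points of the cumulative incidence. It works because participants with a competing event stay in the risk set to 24 months without an event, and nobody's follow-up ends administratively before then.

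**The case against.** Four points can be made for the plan as it stands.

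- **No estimator is fixed.** A reader might infer that the protocol commits the study to publishing an inflated incidence. It does not go that far. Section 8.1 names only hazards, and a statistical analysis plan that is not shown may name an estimator for the absolute risk. This stands, and makes the point conditional. It does not dispose of it: the protocol itself sets the censoring rule, ties it to an outcome defined as incidence, and does not list it among the items left to the analysis plan.
- **The right figure is nearly planned already.** As step 6 shows, the sensitivity analysis recovers the cumulative incidence almost exactly. This also stands, so the dispute is about which figure is primary and what it is called. Presented as a check on informative censoring, it would be read as a robustness bound and not as the answer to objective 1.
- **Censoring answers a sensible question.** Risk while the index stoma remains is a reasonable target when comparing stoma types, and is worth reporting. It is not the proportion of patients affected, so it should carry its own label.
- **The documented effect is small.** Only the 2 to 3 points from deaths rest on the protocol's figures. A reader might infer a much larger excess from the closures mentioned in section 4.7, but those are of loop ileostomies, which objective 1 leaves out and objective 2 does not list. Section 8.1 does foresee restored continuity, but no rate is given for any of the compared types.

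**Conclusion.** The point holds in conditional form. If the figures for objectives 1 and 2 are taken from the censored analysis, they will exceed the proportion of patients who develop a PSH. The direction is certain. On the documented inputs (15% deaths, 30% to 40% incidence) and constant, independent hazards, the excess is 2.2 to 2.8 points. With assumed net closure of 10% to 50% by 2 years it is about 3.5 to 12 points, and it then varies by stoma type. Redo stomas would add to it by an amount the protocol does not allow one to estimate.

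A reader might also infer that the comparisons of surgical steps are invalid. The documents do not support that: censoring competing events is standard for cause-specific hazard ratios, which is what section 8.1 says will be estimated. The weakness is confined to the absolute risks.

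**What to change.** Add to section 8.1: for objectives 1 and 2, the main estimate is the Aalen-Johansen cumulative incidence of PSH at 24 months, overall and by stoma type, with death, restoration of continuity and redo stoma as competing events. Report the censored estimate beside it, labelled as risk while the index stoma remains, and give the cumulative incidence of each competing event by stoma type so that readers can see why the two differ. State that objectives 3 to 6 keep censoring and are reported as cause-specific hazard ratios. The existing sensitivity analysis can stay for the models.

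The cost is a few sentences before database lock, standard software and a little more analysis, with no new data. The headline incidence becomes slightly lower.

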#### 4. Plan of Investigation

#### 4.1 Study schema

#### Figure 1: The study schema for CIPHER (Phase B)

\*The duration of follow-up is for a minimum of 2 and maximum of 4 years

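### The one named check on informative censoring scores a redo stoma done for an unconfirmed hernia as the longest hernia-free time, and carries people past the follow-up they could have had

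*Protocol*

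**What the plan says.** Section 8.1 (Phase B) sets the censoring rule: "Follow-up will also be censored if bowel continuity is restored, if participants have a redo stoma or die". It accepts that this may be informative and names one method: "These circumstances leading to censoring may be informative and sensitivity analyses (setting survival times to the longest observed times) will be undertaken". The same section leaves covariates, modelling strategy and correlated predictors to the SAP, and contemplates a parametric survival model, with Weibull as its example.

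The event needs two things together (section 4.6.1): symptoms on the stoma questionnaire and an anatomical hernia on a usual-care CT. On the CT window: "CT scans taken up to 6 months before or 3 months after the stoma questionnaire is completed will be valid for assessing anatomical PSH". The event time in section 8.1 is "defined as the time when PSH confirmed by imaging". Table 4 schedules the stoma questionnaire at 6 months, 12 months and 6-monthly after that.

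On follow-up, the note to the Phase B study schema states: "The duration of follow-up is for a minimum of 2 and maximum of 4 years". Section 5.1 gives 24 months of recruitment.

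On redo stomas, the Phase A background, writing of emergency admissions for obstruction, strangulation or perforation, adds: "This may necessitate surgery, potentially including revision of the stoma".

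**The concern.** Three different circumstances get the same treatment. After death or restored continuity there is no stoma left to herniate, so holding the person event-free is a sensible competing-risk style analysis. A redo stoma differs, because it may have been done on account of a hernia. If that hernia had not yet been confirmed by questionnaire plus CT, the main analysis censors the person as hernia-free, and the check then assigns the best survival time in the cohort. A check meant to expose informative censoring would instead move the estimate further the wrong way.

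The second issue is the length of the carry-forward. Everyone can be followed for 2 years, but only the earliest recruits for 4. Carrying a late recruit who died or had a closure to the cohort maximum keeps that person at risk after living contemporaries have left.

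At stake is whether a technique effect near the size the study is built to detect would be called robust when it is not.

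**Working it through.** **Scale.** The smallest detectable effect in Table 3 reproduces by Schoenfeld's formula, HR = exp[(z_0.975 + z_power)/√(N × incidence × a(1−a))]. With N = 4000, incidence 40% and a = 0.5, the root is √(4000 × 0.4 × 0.25) = 20. At 90% power, exp(3.2416/20) = 1.176; at 80% power, exp(2.8016/20) = 1.150. The table prints 1.18 and 1.15. That figure is not in dispute. It shows that a shift of 0.07 in the hazard ratio matters.

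**Inputs.**
- From the protocol: 40% hernia at 2 years (section 4.7), about 15% deaths by 2 years (section 5.10), follow-up of 2 to 4 years with uniform entry over 24 months.
- Exponential rates: hernia −ln(0.60)/2 = 0.2554 per year; death −ln(0.85)/2 = 0.0813 per year; sum 0.3367.
- Assumed, because the documents give no figure: the share of hernias revised just before they would have been confirmed, and any closure rate.

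**Redo stoma.** Cox hazard ratios, about 60,000 simulated participants per run. The second run repeats the same set-up independently.

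| True HR | Hernias revised first (unexposed v exposed) | Main | Planned check | Second run: main, check |
|---|---|---|---|---|
| 1.25 | 5% v 5% | 1.24 | 1.21 | 1.25, 1.23 |
| 1.25 | 1% v 3% | 1.21 | 1.18 | 1.23, 1.20 |
| 1.25 | 5% v 15% | 1.10 | 1.03 | 1.11, 1.04 |
| 1.00 | 5% v 20% | 0.85 | 0.80 | 0.85, 0.81 |

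Counting redo as an event gives about 1.23 in the third row (1.23 to 1.26 across runs) and 1.01 in the fourth. Differences of 0.01 to 0.02 between runs are simulation noise: with roughly 45% having an event, the standard error of the log hazard ratio is about 2/√27,000 = 0.012. The gap between main and check is steadier, since both use the same simulated people. In the third row 1.25 − 1.10 = 0.15 is lost in the main analysis, and the check moves a further 1.10 − 1.03 = 0.07 away.

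**Overrun, risk set at year 3, deaths only.**
- Alive, hernia-free and still in follow-up: e^(−3 × 0.3367) × ½ = 0.182.
- Seen to die hernia-free by year 2: (0.0813/0.3367) × (1 − e^(−0.6733)) = 0.118.
- Seen to die in year 3, weighting each time s by the chance (4 − s)/2 of still being followed: 0.027.
- Planned rule: 0.145/(0.145 + 0.182) = 44% of those counted at risk are dead.
- Own planned end: 0.2414 × (1 − 0.3642) × ½ = 0.077, and 0.077/(0.077 + 0.182) = 30%.
- With the hernia rate multiplied by 1.25, the same sums give 47% and 32%. Simulation gave 47% against 32% to 33%, and at 3.75 years 82% against 39%.

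**Overrun, effect on estimates.**
- Cox: with closure 10% v 40% by 2 years (assumed) and true HR 1.00, 0.757 under the planned rule against 0.768 with own planned end. With closures unrelated to technique and true HR 1.25, 1.251 against 1.252.
- Exponential rate ratio, same differential closure and true HR 1.00: 0.704 against 0.757. Repeat runs gave 0.69 v 0.75 and 0.67 v 0.73. The distance from 1.00 mostly reflects closure removing hernia risk and is not itself an error; the gap between the two rules is the overrun.
- Cumulative incidence, deaths only. At 2 years both rules give the true value, (0.2554/0.3367) × (1 − e^(−0.6733)) = 37.2%. Near year 4 (3.9 years) the true value is 0.7586 × (1 − e^(−1.313)) = 55.5%; the planned rule gives 51.4% and own planned end 55.1%.

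**The case against.** Much of the opposing case stands.

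- **Death and closure.** A reader might infer that the rule is wrong for all three circumstances because it tests one direction only. It is not. Scoring a death or closure as a hernia would be implausible, and event-free is the right direction for both.
- **How often redo means hernia.** A reader might infer that redo stomas usually signal a hernia. The documents do not say so. The Phase A sentence concerns some emergency admissions and says surgery may potentially include revision; Phase B section 2.2.1 calls those complications rare. A redo after confirmation is already an event, so only revisions before confirmation are affected.
- **Size.** The large shift needs a threefold difference between techniques that no source supports. With equal shares the check barely moves, and most of the bias in the large case lies in the main analysis.
- **Direction.** A reader might infer that the check always pulls towards no effect. In the null example it moves away, from 0.85 to 0.80.
- **Overrun.** Its effect on a Cox model is slight, and the incidence objective in section 3 is set at 2 years, where there is none.
- **Reading and completeness.** Section 8.1 states neither the event status at the imputed time nor that one cohort-wide maximum is meant, and an SAP not shown may add further analyses.

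The objection does not remove the narrow point. Section 8.1 names a specific rule and applies it to redo stoma. For an unconfirmed hernia that rule points the wrong way, and nothing named points the other way.

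**Conclusion.** The point holds in limited form, as a cheap improvement to a stated rule.

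For redo stoma the check cannot reveal the bias it is there to find. If hernia-driven revisions before confirmation differ by technique, it lies further from the truth than the main analysis: by about 0.03 in the hazard ratio at 1% v 3%, and about 0.07 at 5% v 15%. Those shares are assumptions. If revision is unrelated to technique, the harm is small.

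Carrying people to the cohort maximum is a lesser fault. It is worth up to about 0.015 on a Cox hazard ratio, more on a parametric fit if closure differs by technique, and about 4 percentage points on incidence near year 4 (55.5 − 51.4). It does not affect 2-year incidence.

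All of this rests on the natural reading, event-free to about 4 years. The documents do not support saying that the main result will be biased, or that no other check will be done.

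**What to change.** In section 8.1, replace the single rule with two runs.

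(a) Carry closure, redo stoma and death forward event-free only to the participant's own planned end of follow-up, that is, study close minus surgery date. State the event status explicitly.

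(b) Add a run that counts a redo stoma as a hernia event on its date, unless records show another reason.

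The cost is a wording change and a few extra model fits, which should need only dates the censoring rule already requires plus any recorded reason for the redo. The drawback of (b) is that some redos unrelated to hernia will be counted as events. In a run with 5% such redos by 2 years and true HR 1.25, the estimate went from 1.26 to 1.24. Report (b) as a bound beside (a), not as the estimate.
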